where Y_{ij} is the outcome measure (Caregiver Burden and Anxiety) for participant (i) at time (j) where j is an indicator for time (baseline, 4 weeks, 8 weeks, 12 weeks, 16 weeks and 20 weeks). β_0 is the population mean level of the outcome measure prior to the TLC intervention, β_1 fixed effect for time independent of intervention, X_{ij} is the intervention status (pre-TLC or Post-TLC/Follow-up) at timepoint j, and β_2 is the intervention treatment effect. Random effects include individual-level intercept (ζ_{0i}), individual-level slope of change over time ($\zeta_{1i} T_{ij}$), and ϵ_{ij} for residual error of each outcome measure. Our hypotheses for Aim 2 are summarized here:

Over time, we expect intervention engagement to produce more positive wellbeing, with time satisfaction as the mechanism through which TLC achieves its effect.

- H1:** Burden & anxiety will be lower among the treatment group compared to those in control/waitlist condition (direct effect)
- H2:** Time-use satisfaction will be higher among the treatment group compared to those in control/waitlist (direct effect)
- H3:** Higher time-use satisfaction will be associated with lower burden & anxiety (direct effect)
- H4:** Higher time-use satisfaction will mediate the effect of the intervention on burden and anxiety (direct & indirect effect)

H1: Burden & anxiety will be lower among the treatment group compared to those in control/waitlist condition (direct effect)

Figure 2: Anticipated results for Wellbeing with TLC

Our primary outcome will test the hypothesis that there will be significant change in “caregiver burden” or “anxiety” immediately post intervention. Figure 2 shows the anticipated results with no change during the run-in period, increase in wellbeing in Group A during the intervention but not WLC. Group B then shows increased wellbeing during TLC, with Group A maintaining or slight decrease in “caregiver burden” or “anxiety” over time. With the planned 120 participants (60 per group), we will be able to detect small to medium effect sizes on the two outcomes with greater than 90% Power (see below). Intent-to-treat analyses (ITT) will be performed on non-completers using a terminal score for both “caregiver burden” and “anxiety” scores.

H2: Time-use satisfaction will be higher among the treatment group compared to those in control/waitlist (direct effect)

[figure not shown]

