We assume clinically relevant small to medium effect sizes in the main outcomes of interest corresponding to 4-6.5 mean change on the total "caregiver burden" outcome and 1.0-1.4 mean change on the "anxiety" outcome. Power and sensitivity analysis were computed in GPower using RMANOVA finding a total sample of 116 would be sufficient to achieve

power of greater than 90% to detect these effect sizes. Therefore, we will aim to have a final sample size of 120 (60 in each sequence) with a 25% over-recruitment to account for study attrition providing a total sample size of 150.

Sample size and sensitivity analyses for mediation analyses are based on empirical estimates conducted by Fritz and MacKinnon (2007).¹²¹ Assuming medium effects for each of the two parts of the indirect pathways (i.e. TLC->Time-use and Time-use->Wellbeing) in Figure 3, a sample size of 75-120 will provide greater than 80% Power (Sobel148 medium-medium effects) at $p=0.05$.

Missing Data

We will explore missing data patterns in SPSS using the Missing Value Analysis tool. We will specify the pattern fixed effects and interactions utilizing Little's test for Missing Completely at Random. In keeping with an intent-to-treat standard and assuming maximum likelihood estimation, we will use all available data for analyses. It is not necessary to eliminate observations from participants who subsequently drop out, nor is it necessary to impute individual observations. Both practices can bias estimation and distort variability. The maximum likelihood estimates given the observed data points are the values most likely to have generated the complete ensemble of observed sample data under the assumed model. Systematic missingness (as determined by missing data patterns) may be included in our mixed effects model. Potentially non-ignorable missing data will be investigated using multiple imputation sensitivity analyses under a diverse set of covariate predictors. To minimize loss of scale scores due to missing items in a computed scale, we will prorate the respondent's score based on available items. If a respondent is missing more than 30% of the items in a computed score for the primary outcome variables, we will code the scale score as missing.

Note: feasibility is another primary outcome of the pilot test. Feasibility-related analyses are discussed at the end of this document, since the focus on feasibility and the analytic strategies to measure feasibility are shared across Aims 1, 2, and 3.

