Figure 5. RE-AIM Dimensions, Suggested Questions for Evaluating Intervention, and Proposed Study

Dimension	Suggested Questions	Proposed Study
Reach	What percent of potentially eligible participants a) were excluded, b) took part and c) how representative were they?	Tracking and analysis of recruitment and eligibility data
Efficacy or Effectiveness	What impact did the intervention have on a) all participants who began the program; b) on process intermediate, and primary outcomes; and c) on both positive and negative (unintended), outcomes including quality of life?	Hypothesis-driven statistical analyses identifying direct and indirect effects of the intervention's efficacy (Aim 2)
Adoption	What percent of settings and intervention agents within these settings a) were excluded, b) participated and c) how representative were they?	Comparison of provider sample characteristics (Aim 3) to population of respite providers

Implementation	To what extent were the various intervention components delivered as intended, especially when conducted by different (nonresearch) staff members in applied settings?	Qualitative themes describing provider comments about barriers and likelihood of implementation (Aim 3)
Maintenance	
What were the long-term effects (minimum of 6-12 months following intervention)?
 
What was the attrition rate; were drop-outs representative; and how did attrition impact conclusions about effectiveness?
 
To what extent were different intervention components continued or institutionalized? How was the original program modified?
	
Initial maintenance or attenuation of intervention efficacy (after 2 months) will be assessed by exploratory analysis comparing post-intervention wellbeing to follow-up wellbeing (Aim 2)
 
Attrition rates will be calculated and described; missing data will be explored as a potential moderator of intervention efficacy (Aim 2)
 
Stakeholders (Aim 1), caregivers (Aim 2), and providers (Aim 3) will all provide information on how the intervention might be further modified.

Table adapted from: www.re-aim.org

Table 1: Amendments submitted and approved by IRB throughout study

Amendments	Date	Description
Adding RA	9/2/2019	Adding new study personnel
Changing Staff on Project	2/18/2019	Adding new study personnel

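### The one firm commitment on non-ignorable missing data is multiple imputation with varied covariates, which as described assumes missing at random like the primary model and cannot show sensitivity to departures from it

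*Combined protocol and SAP*

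**What the plan says.** The Missing Data section sets the main approach: "In keeping with an intent-to-treat standard and assuming maximum likelihood estimation, we will use all available data for analyses". For data that may be missing for reasons tied to the unseen scores, it commits to one analysis: "Potentially non-ignorable missing data will be investigated using multiple imputation sensitivity analyses under a diverse set of covariate predictors". It names no shift, reference-based rule, selection model or tipping point.

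Four other provisions bear on the point:

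- Missing Data, on patterns: "We will specify the pattern fixed effects and interactions utilizing Little's test for Missing Completely at Random".
- Missing Data, just before the imputation sentence: "Systematic missingness (as determined by missing data patterns) may be included in our mixed effects model".
- Analysis, under H1: "Intent-to-treat analyses (ITT) will be performed on non-completers using a terminal score for both" burden and anxiety. The term is not defined.
- Figure 5, Maintenance row: "missing data will be explored as a potential moderator of intervention efficacy (Aim 2").

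Power and Sample Size allows for loss by a "25% over-recruitment to account for study attrition providing a total sample size of 150", from a final target of 120.

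**The concern.** Maximum likelihood on available data is valid if withdrawal depends only on data that are observed and in the model. A sensitivity analysis for non-ignorable withdrawal has to relax that assumption. It must let the unseen scores of caregivers who left differ from those of otherwise similar caregivers who stayed. Adding or swapping covariates may make missing at random more plausible, but that difference stays fixed at zero in every run.

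Differential withdrawal is credible here. The Procedures section says the groups differ in the amount and timing of coaching. Figure 4 sets a benchmark for intervention-related drop-out (at most 10%) separately from design-related dropout (at most 10%), so the plan itself allows for people leaving because of the intervention. If treated leavers do not keep the benefit, the primary model and the covariate-varied imputations carry nearly the same bias. Their agreement could then be taken for robustness.

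**Working it through.** **1. The plan's own figure.** 120 × 1.25 = 150, as stated. The allowance equals a loss of 30/150 = 20% of those recruited. (Had 25% been meant as a loss rate, 120/0.75 = 160.)

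**2. What the stated imputation does.** Each missing score is drawn from a model fitted to observed scores, given arm and the chosen predictors. A different predictor set gives a different prediction, but leavers and stayers with the same predictor values always share one distribution. No run departs from missing at random.

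**3. Size of the possible bias.** Let p be the share of Group 1 that leaves, and δ the amount by which their scores are worse than missing at random predicts, with Group 2 unshifted. For a between-group comparison at one visit:

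effect in all randomised = effect under missing at random + p × δ (a benefit is negative)

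Assume p = 0.20 and no benefit in treated leavers, so δ equals the size of the effect. Take the plan's effects as those in stayers, which is also an assumption:

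- Burden: 4 × 0.80 = 3.2; 6.5 × 0.80 = 5.2.
- Anxiety: 1.0 × 0.80 = 0.8; 1.4 × 0.80 = 1.12.

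**4. Simulation.** The assumptions are 75 per arm, 1,500 runs, one follow-up score, SD 14, correlation 0.6 with baseline, and 20% dropout depending on baseline and a second covariate. The effect is −4 before any shift, and δ applies to Group 1 leavers only. The documents give no SD, so 14 is illustrative.

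| δ | Truth | Likelihood, available data | MI, missing at random | Same MI, extra covariate | Delta-adjusted MI |
|---|---|---|---|---|---|
| 0 | −4.00 | −4.06 | −4.07 | −4.04 | −4.05 |
| 4 | −3.21 | −4.03 | −4.04 | −4.05 | −3.26 |
| 10 | −2.02 | −3.96 | −3.96 | −3.96 | −1.98 |

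Simulation error is about 0.05: residual SD 14 × √(1 − 0.36) = 11.2; standard error per run 11.2 × √(2/60) = 2.04; 2.04/√1500 = 0.05. The three missing-at-random columns agree with each other to within that error and miss the truth by about 0.8 (δ = 4) and 1.9 (δ = 10). The delta-adjusted column was given the true δ. It shows that the method can represent the departure, not that δ can be learned from the data.

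**5. How far a delta grid must run.** The point estimate reaches zero at δ = effect/p:

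| Loss p | Burden 4 to 6.5 | Anxiety 1.0 to 1.4 |
|---|---|---|
| 10% | 40 to 65 | 10 to 14 |
| 20% | 20 to 32.5 | 5 to 7 |
| 25% | 16 to 26 | 4 to 5.6 |

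Statistical significance is lost at a smaller δ, which cannot be computed without the SD. A grid stopping at the planned effects would move the estimate by at most 0.20 × 6.5 = 1.3 burden points or 0.20 × 1.4 = 0.28 anxiety points, and might never reach a change of conclusion.

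**The case against.** The strongest reply is that the plan has more than this one analysis. The pattern terms in the mixed model are a pattern-mixture type of provision, which can address non-ignorable dropout. The terminal-score analysis need not agree with the primary model. A simulation took the terminal score to be the last observed score, with 20% dropout, a stayer effect of −4, SD 14, correlation 0.6, no time trend and no benefit in treated leavers. The truth was −3.17, the terminal-score analysis gave −3.17, and imputation from baseline alone gave −3.98. Nor is imputation always powerless: with one post-baseline visit observed in leavers, and half the benefit visible by then (an assumption), it moved to −3.83. The trial has six assessments plus daily and log-in data.

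Much of this stands. A reader might infer that imputation is the plan's only safeguard; the provisions above show that it is not. They are too loose to fill the gap, however. The pattern terms are optional, with no patterns or identifying restriction stated, and Little's test addresses only missing completely at random. The terminal score matched the truth because, with no trend, carrying a baseline score forward is the same as no benefit. In general it is one fixed rule that could freeze an early gain. It also sits awkwardly with the Missing Data section, which calls imputing individual observations unnecessary and a possible source of bias.

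Three other strong readings are not supported:

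- That the plan should test for non-ignorable dropout. Observed data cannot do so; they allow only an assessment of sensitivity.
- That the effect will be overstated by a fifth of its size in stayers. The 20% is a recruitment allowance over the whole study, not a forecast; loss by arm at the H1 comparison is not given, and the planned effects are not stated to be effects in stayers.
- That the moderator analysis in Figure 5 is improper. It is exploratory and claims no randomised comparison.

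**Conclusion.** The point holds in this form: the analysis firmly promised for non-ignorable missing data is, as described, a missing-at-random analysis, and the alternatives are optional, undefined or exploratory. Multiple imputation is not itself at fault, since it can be run with a departure built in; the plan states none.

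The 3.2 to 5.2 burden and 0.8 to 1.12 anxiety figures illustrate one scenario and do not estimate the bias in this trial. The large deltas in step 5 also cut the other way: a clear result could prove hard to overturn, and the plan as written has no means of showing that. This is a gap in the sensitivity analysis that should be closed before the data are analysed. It is not a fault in the choice of primary model.

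**What to change.** Replace the imputation sentence in Missing Data with a delta-adjusted multiple imputation of burden and anxiety:

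- Impute under missing at random using all observed visits. Then worsen imputed Group 1 scores after withdrawal by δ from 0 upward, leaving Group 2 unchanged. Fit the planned model to each completed data set and pool.
- Extend the grid beyond 6.5 burden and 1.4 anxiety points until the H1 conclusion changes, and report that tipping point for each outcome.
- Add a reference-based version in which Group 1 leavers follow Group 2's trajectory before its intensive coaching. Procedures starts that coaching at week 9 and Study Design at week 12; the two passages must be reconciled before the reference window is coded.
- Report attrition by arm, visit and reason. Figure 5 already plans to describe attrition rates, so only the split is new.
- Keep the moderator analysis in Figure 5, but label any missingness-by-treatment result as exploratory and non-randomised.

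The cost is SAP wording and a few extra imputation runs. The primary analysis is unchanged.
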